This study is designed as a randomized control trial. Figure 1 shows the time line for the study. There will be four groups of subjects, (1) normal weight-bearing with massage (WB-M), (2) normal weight bearing without massage (WB-C) (3) ULLS, no massage (control, U-C), and (4) ULLS with massage (U-M). We expect to recruit 140 subjects to in order in fully enroll 128 (32 per group, n = 3 per group for attrition). For measurement of protein synthesis, participants will ingest three 50 mL doses of heavy water (2H2O) for the first two days and the dose will decrease to two 50 mL doses per day (a total of 1000 mL of heavy water for each subject over the course of the trial). 3-4 blood draws will be taken on days 2, 5, 7, and 9 and each will be drawn at the same time each day. Subjects in U-C and U-M groups will have their left leg immobilized and suspended using a hinged knee brace. Those immobilized will be required to wear the brace and use crutches at all times, except while showering and sleeping. Immobilization will begin on day 2 and will continue until the end of the study (day 9). Members of the research team will use a custom-made device to massage the quadriceps region of subjects' left leg and leave the right leg unaffected in the WB-M and U-M groups. Massage treatments will begin on day 3 and will take place every other day (day 5, 7, 9) until the end of the study. A baseline muscle biopsy of the vastus lateralis will be taken from the right leg on day 2, prior to the first massage. Muscle biopsies will then be taken from both legs 4-6 hours after the last massage on day 9, and the muscle tissue will be frozen for further examination. (See Figure 1). Sham treatment for the WB-C and U-C groups will include us touching the skin using a light brushing technique.

For the weight bearing groups as comparison groups, they will also have to drink deuterium oxide heavy water over 9 days which is associated with 3-4 blood draws but will not have to wear a brace or use crutches. Weight bearing control groups will only have one biopsy taken on day 9 while weight bearing massage groups will have two biopsies taken (day 2- right leg, and day 9- left massaged leg). This will still allow for effective comparison between groups and will reduce burden on these participants. We will enroll the weight bearing groups after immobilization groups to ensure that those interested in the study will not drop out after possible randomization into the immobilization group.

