Subjects will report to the Human Performance Lab, in room B04A of the Multidisciplinary Science building. A custom-made cyclic compressive loading (CCL) device will be used to apply a mechanical load to the left thigh starting on day 3. The knee immobilizer will be removed, and the subjects will be positioned right lateral recumbent with their left hip and leg slightly flexed and the left leg supported by a wedge to maintain anatomical position in the frontal plane. The CCL device will be a commercially available massage roller instrumented with a strain gage to measure applied load. Massage application using a 35 newton load will be applied for 15 minutes every other day over the course of 7 days (days 3, 5, 7, and 9). The CCL device will be placed 10cm proximal to the superior pole of the patella over the vastus lateralis muscle of the left leg, and a normal force of 35N will be applied while rolling the device proximally along the length of the vastus lateralis at a rate equal to one muscle length over 2 seconds. Without interruption, the direction of the massage will then be reversed and the same load and loading rate will be applied proximal to distal. Thus, one complete cycle of massage to the vastus lateralis will take 4 seconds, corresponding to a duty cycle of 0.25Hz. Massage will continue for 15 minutes, resulting in approximately 225 complete cycles. Sham treatment (WB-C and U-C) groups will receive a light touching on the skin using a light brushing technique.

We have previously shown that the beneficial effects of massage can be optimized by application of the appropriate dose¹², including considerations for timing of massage application¹³, duration of massage¹⁴ and the magnitude of applied load.^{5,12} Therefore, we have used allometric scaling laws to calculate optimal loads based on our early investigations demonstrating effectiveness of massage for limiting inflammation and accelerating recovery after injury in rabbit skeletal muscle.¹⁵ We have used this method to successfully scale the optimized loads to rats⁵ and have applied the same methods to calculate the appropriate loads for human massage. We have determined that the optimal load for human vastus lateralis is a normal force of 35N.

Muscle Biopsies:

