On day 2 of the study (after the first two days of heavy water intake), a baseline muscle biopsy will be taken from the vastus lateralis muscle of the right leg. Subjects will be instructed not to eat or drink anything for breakfast the last day of the study when they come in for the last massage and the biopsies. Subjects will be provided a light breakfast consisting of a choice of bagel with cream cheese or

granola bar or muffin with banana and orange juice. Four hours after the last bout of massage one muscle biopsy will be taken from the left and the right vastus lateralis each. Biopsies (100-300 mg tissue) will be taken by one of the two physicians on the study or the physician assistants listed in the protocol. The tissue will be frozen for analysis by the experimenters. In exercise literature a waiting period of about 2-6 hours is what is shown to demonstrate changes in the expression of genes associated with muscle size regulation.^{16,17} In an effort to respect the subjects' time, a waiting period of 4-6 hours was decided. The subjects are allowed to walk around after the massaging, but are asked to refrain from exercising for the 4 hours in between the massage treatment and the muscle biopsy.

Muscle Biopsy Procedure:

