A muscle biopsy sample will be obtained from the vastus lateralis. The biopsy procedure will proceed as follows for each subject taking approximately 45 minutes. Subjects will report to the procedural room located in the Center for Clinical and Translational Science (CCTS). Subjects will lie down and have a 1 inch by 1 inch portion of hair removed with a disposable razor on the outer surface of the thigh as necessary. The site will then be cleaned with alcohol followed by the application of Betadine. A local anesthetic (1% Xylocaine HCl, 3cc) will be used to numb an area the size of a quarter on the site of the outer thigh over the vastus lateralis muscle approximately a hand width above the knee using a 23-gauge, 1 inch needle, subcutaneously. Anesthetic will further be injected into the subcutaneous space of the numbed area from the muscle to the dermis. After 5-10 minutes, a sterile scalpel will be used to test for numbness before the procedure proceeds. In our experience, 5 minutes is adequate to sufficiently numb the area for the biopsy procedure. A ¼ inch wide incision will be made through the skin in the center of the anesthetized area with a sterile, single-use, #11 disposable scalpel. The incision needs to perforate the fascia of the vastus lateralis muscle sufficiently to allow for subsequent entry of the biopsy needle. The depth of the incision will be adjusted to accommodate estimated subcutaneous fat depth. A sterile 5 mm Berkstrom biopsy needle (Pelomi Industries, Denmark) will be passed through the ¼ inch incision into the muscle and a small piece (the size of a pencil eraser, equal to ~ 100-300 mg) of muscle will be removed. The angle of entry for the biopsy will be medial to lateral. The biopsy team will use the suction biopsy technique, whereby a small amount of suction with a Monoject 60cc syringe attached via sterile tubing to the end of the trocar will be applied to the needle prior to closing of the trocar, which enhances the investigators' ability to maximize the amount of muscle obtained. A conchotome may also be used to remove the muscle. Manual pressure will be applied to the wound until bleeding stops. The muscle biopsy site will be cleaned with an alcohol preparation to clear all betadine and standard procedures will be used to close the wound. The biopsied area will be covered with gauze and a pressure wrap applied. The muscle tissue obtained will be divided into pieces and processed for analysis of muscle phenotype.

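### The massage and the muscle biopsy are located by different landmarks, so nothing in the protocol ensures that the day-9 left-leg sample comes from massaged muscle

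*Protocol*

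**What the plan says.** All of these are in the protocol, mostly under Research Procedures.

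- **Massage, start:** "The CCL device will be placed 10cm proximal to the superior pole of the patella over the vastus lateralis muscle of the left leg".
- **Massage, outward stroke:** a 35 N load is applied "while rolling the device proximally along the length of the vastus lateralis at a rate equal to one muscle length over 2 seconds".
- **Massage, return stroke:** "the same load and loading rate will be applied proximal to distal". No distal end point is given.
- **Muscle Biopsies:** "Four hours after the last bout of massage one muscle biopsy will be taken from the left and the right vastus lateralis each". Either of two physicians, or one of the listed physician assistants, may take the sample.
- **Muscle Biopsy Procedure, site:** local anesthetic is given "over the vastus lateralis muscle approximately a hand width above the knee", and the "incision will be made through the skin in the center of the anesthetized area". "The angle of entry for the biopsy will be medial to lateral"; no proximal angling is mentioned.
- **Study Design:** the team will "use a custom-made device to massage the quadriceps region of subjects' left leg", with no limits to the region.

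The massage start has a bony landmark and a distance in centimetres; the biopsy site has neither. No section requires the biopsy to fall within the massaged segment or the distance to be recorded.

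**The concern.** The Objectives section asks whether a specified load on one muscle changes protein synthesis, cross-sectional area, satellite cells and muscle damage. Three of the four outcomes used for sample size in the SAP (CSA, MyoKsyn and Rab27 mRNA) appear to be read from the biopsy. If massage acts locally and the sample comes from outside the loaded segment, the massage-versus-sham difference shrinks towards zero. A finding of no muscle damage would also say little if the tissue examined had not received the load. A site measured by hand width can also vary between operators. The analysis cannot correct for any of this unless the site is recorded.

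**Working it through.** **The plan's own figures.** The only derived number in the Massage section is the cycle count: 15 × 60 s ÷ 4 s = 225, which reproduces. The documents state no distance between biopsy site and stroke start. The SAP's n per group for CSA, MyoKsyn and Rab27 (21, 19, 22) is reproduced to within one by a two-sample t-test calculation at two-sided 5% and 80% power (20.0, 19.5 and 21.2, which round up to 21, 20 and 22). The SAP states neither alpha nor target power, so both are assumed.

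**Geometry.** Inputs: stroke start 10 cm above the superior pole (protocol); hand width *h* = 7 to 12 cm (assumption); the knee landmark lies *k* = 0 to 6 cm below the superior pole (assumption).

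Offset of biopsy from stroke start = *h* − *k* − 10. A negative value is distal to the start.

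| Hand width (cm) | k = 0 | k = 2 | k = 4 | k = 6 |
|---|---|---|---|---|
| 7 | −3 | −5 | −7 | −9 |
| 8 | −2 | −4 | −6 | −8 |
| 9 | −1 | −3 | −5 | −7 |
| 10 | 0 | −2 | −4 | −6 |
| 11 | +1 | −1 | −3 | −5 |
| 12 | +2 | 0 | −2 | −4 |

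Of the 24 combinations, 20 are distal to the start, 2 fall exactly on it and 2 are proximal, by 1 and 2 cm. Both proximal cases need a hand wider than 10 cm measured from the superior pole itself. The grid shows what the wording allows; it is not a probability.

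**Illustrative dilution.** Suppose a share *f* of left-leg samples in the massaged group carries no massage effect. The expected difference becomes (1 − *f*) × the SAP value, with the SD held fixed (mixing would add variance, ignored here). SAP differences are 10, 70 and 150; SDs are 11, 76 and 170. At *f* = 0.25 the differences are 7.5, 52.5 and 112.5. Power is from a noncentral t-test, two-sided 5%, n = 22 per group (SAP):

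| f | CSA | MyoKsyn | Rab27 mRNA |
|---|---|---|---|
| 0 | 0.84 | 0.85 | 0.82 |
| 0.25 | 0.60 | 0.61 | 0.57 |
| 0.50 | 0.31 | 0.32 | 0.30 |

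With *f* = 0.25 and the 32 per group given in the protocol's Study Design section, power is 0.74–0.78. For a massage main effect comparing 44 with 44 (two groups of 22 on each side, equal effect in both loading states), it is 0.87–0.89.

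**The case against.** A reader might infer that the biopsy does lie below the massage and that the tissue was never massaged. The documents do not support that. It would need a hand width, a definition of the knee, a roller contact width and a distal limit to the return stroke, and none of these is given. The biopsy level is itself only approximate, and a wide hand measured from the superior pole puts the sample slightly inside the stroke. The description of rolling along the length of the vastus lateralis at one muscle length per pass can also be read as whole-muscle coverage. All of this stands, so the claim is limited to what may happen. It does not remove the point: the whole-muscle reading is hard to square with a start 10 cm above the patella if the muscle extends below that level, so the massage text needs clarifying too.

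A reader might also take the power figures as an estimate of loss. They are not. The miss rates have no source in the documents. Zero effect just outside the path is a worst case, particularly as the trial itself looks for a crossover effect in the other limb. The planned analysis is a Two Way ANOVA, under which the loss can be smaller, as the 44-versus-44 figure shows. If the six-subject pilot used the same biopsy site (not stated), some dilution is already in the expected differences.

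Finally, the same site wording applies to every subject, so the expected error is attenuation rather than bias between arms. That is correct, and it is why the concern is about dilution.

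**Conclusion.** The point holds in this form: the protocol does not locate the biopsy relative to the massaged segment, and its wording allows a sample at or beyond the distal edge of the loaded muscle. Under the stated assumptions (hand width 7–12 cm, knee landmark 0–6 cm below the superior pole) the sample ranges from about 9 cm distal to 2 cm proximal of the stroke start. The consequence is possible dilution of the massage contrast in tissue outcomes and a less informative muscle-damage result. How large that is cannot be determined from the documents; the power figures show only that the margin is thin for a two-group comparison at 22 per group. No sample-size or power figure in the SAP is shown to be wrong by this.

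**What to change.** Reconcile the Massage and Muscle Biopsy Procedure sections. State both ends of the stroke and the biopsy level in centimetres from one common bony landmark, so that the sample is known to lie within the massaged segment. The choice of location is the sponsor's. Use the same level in massage and sham groups, and record the measured distance at each biopsy.

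The direct cost is small: a few words of protocol text, a tape measure, a skin mark and one extra data field. The real cost is timing. The demographic table in the continuing-review section already counts 49 participants (1 + 3 + 2 + 3 + 12 + 26 + 1 + 1), and Study Design enrolls the weight-bearing groups after the immobilization groups. A change made now could fall mainly on the weight-bearing groups and confound sampling site with the ULLS factor. Samples taken before and after any change should therefore be flagged, all samples kept in the main analysis, and a sensitivity analysis run by site or period. Samples whose site was not recorded should not be dropped: since no recording was required, that could remove most of the earlier data.

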- Which risks may affect a subject's willingness to participate in the study?
- Describe likely adverse effects of drugs, biologics, devices or procedures participants may encounter while in the study.
- *Qualitative research* - describe ethical issues that could arise while conducting research in the field and strategies you may use to handle those situations.
- Describe any steps to mitigate these risks.

Benefits

- Describe potential direct benefits to study participants – including diagnostic or therapeutic, physical, psychological or emotional, learning benefits. This cannot include incentives or payments.
- State if there are no direct benefits.
- Describe potential benefits to society and/or general knowledge to be gained.

Describe why potential benefits are reasonable in relation to potential risks. If applicable, justify why risks to vulnerable subjects are reasonable to potential benefits.

There are some potential risks associated with the procedures presented in this protocol.

Muscle Biopsies: With the biopsy procedures, there is a risk of bleeding, bruising, pain, infection, and scarring of the skin. Bleeding could rarely result in development of a hematoma. Pain and soreness usually resolves within 24-48 hrs post-procedure. Numbness of the skin near the biopsy site may occur and is usually temporary, but this numbness may persist indefinitely. An allergic reaction to the anesthetic also may occur but is rarely seen.

Heavy Water (2H₂O): The only side effect reported by others is (in rare subjects) a sensation of dizziness or vertigo soon after the first dose. This is presumed to be due to a disequilibrium between H₂O and 2H₂O in the inner ear, and some subjects are sensitive to this. This side effect, when it occurs, goes away and the initial dosing will occur in the CCTS where subjects are monitored.

Blood Draws: With drawing blood, there is a risk of soreness, bruising, pain, infection, bleeding, and fainting. Any pain, bruising, or soreness will usually resolve without any treatment. Any infection, bleeding, or fainting can be treated.

Massage: The only side effect reported from massage is possible soreness during and/or after the session. It will go away with or without treatment within 24-48 hours so treatment is not required.

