Immobilization: With use of the knee brace there is a risk of chaffing, muscle atrophy of the immobilized leg, and muscle soreness of the non-immobilized leg. It is important to note that all effects with use of the knee brace are reversible.

Participants will receive no personal benefit by becoming involved with this study. However, subjects are helping the investigators gain knowledge to better understand the effect of massage on healthy human muscle and to possibly help identify therapies associated with massage.

Available Alternative Opportunities/Treatments

Describe alternative treatments or opportunities that might be available to those who choose not to participate in the study, and which offer the subject equal or greater advantages. If applicable, this should include a discussion of the current standard of care treatment(s).

Participation in this study is strictly voluntary. There are no other alternative treatments, procedures, or choices for the subjects except for not to participate in the study.

[Back to Top](#)

Records, Privacy, and Confidentiality

Specify where the data and/or specimens will be stored and how the researcher will ensure the privacy and confidentiality of both. Specify who will have access to the data/specimens and why they need access.

Describe how data will be managed after the study is complete:

- If data/specimens will be maintained, specify whether identifiers will be removed from the maintained information/material.
- If identifiers will not be removed, provide justification for retaining them and describe how you will protect confidentiality.
- If the data/specimens will be destroyed, verify that this will not violate [retention policies](#) and will adhere to applicable facility requirements.

If this study will use de-identified data from another source, describe what measures will be taken to ensure that subject identifiers are not given to the investigator.

If applicable, describe procedures for sharing data/specimens with collaborators not affiliated with UK.

For additional considerations:

[Return of Research Results or Incidental Research Findings](#)

[HIPAA policies](#)

[FERPA policies](#)

[Procedures for Transfer agreements](#)
[Information regarding multi-site studies](#)
[NIH Genomic Data Sharing \(GDS\) Policy](#)
[Digital Data](#)

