Risk Assessment: A serious adverse event (AE) is defined as either fatal or life-threatening, requires inpatient hospitalization or prolongation of an existing hospitalization, results in persistent or significant disability/incapacity, is medically significant or requires intervention to prevent one or other of the outcomes listed above. This study is greater than minimal risk.

Grading scale for AE intensity:

Mild: Discomfort noticed but no disruption of normal daily activity.

Moderate: Discomfort sufficient to reduce or affect normal daily activity.

Severe: Incapacitating with inability to work or perform normal daily activity.

Attribution scale for AE reporting:

Probable: AE is related to the procedure (biopsies), including pain, bleeding, infection, and death, if death resulted from one of the aforementioned complications.

Possible: AE follows the biopsy within a reasonable period (within 7 days), but may have been produced by other factors.

Remote: AE does not follow the biopsy within a reasonable period (more than 7 days) and could readily have been produced by other factors.

Unrelated: AE is judged to be clearly due to extraneous causes and does not meet the above criteria.

Monitoring Plan Monitoring for adverse events will be conducted in real-time by the principal investigators and study coordinator. Risks involved with this study are considered greater than minimal risk.

AE Reporting Serious AEs will be reported verbally to the IRB and CCTS within 24 hours and in writing within 48 hours of the event. Unanticipated events will be reported to the CCTS in real time and to the IRB no later than 48 hours after the event. Annual reporting of adverse events will be conducted with the IRB annual review/renewal according to their protocol. These reports will also be forwarded to the CCTS. The CCTS Administration will be informed within 15 days if for any reason the IRB or any other body temporarily or permanently suspends the study.

Data Accuracy and Protocol Compliance All protocols involving human subjects will be directly supervised by the PI or her colleagues to assure compliance. All samples will be coded to eliminate bias. Detailed plans for maintaining subject confidentiality are described in the consent form.

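### The only adverse event attribution scale refers to the biopsy alone, so events from the other study procedures have either no fitting category or no recorded cause

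*Protocol*

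**What the plan says.** The Data and Safety Monitoring section of the protocol gives a single scale, headed "Attribution scale for AE reporting". The heading does not limit it to biopsy events, and no second scale appears in the documents. It has four levels:

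- The highest is worded "Probable: AE is related to the procedure (biopsies), including pain, bleeding, infection, and death" (the death clause is limited to deaths from those complications).
- The next is set by timing: "Possible: AE follows the biopsy within a reasonable period (within 7 days), but may have been produced by other factors".
- Remote is also set by timing. It is meant for events beyond that 7-day limit for which another explanation is easy to find.
- The lowest is a residual level: "Unrelated: AE is judged to be clearly due to extraneous causes and does not meet the above criteria".

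The Potential Risks & Benefits section covers five sources of harm: biopsy, heavy water, blood draws, massage and immobilization. For heavy water it names, in rare subjects, "a sensation of dizziness or vertigo soon after the first dose". For immobilization it begins "With use of the knee brace there is a risk of chaffing, muscle atrophy of the immobilized leg" and adds soreness of the other leg. Massage may cause soreness. Blood draws may cause soreness, bruising, pain, infection, bleeding and fainting.

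The biopsy schedule differs by group. The two suspension groups (U-C and U-M) and the weight-bearing massage group (WB-M) have a biopsy on day 2 and again on day 9. For WB-C the Study Design section says: "Weight bearing control groups will only have one biopsy taken on day 9".

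**The concern.** An attribution scale should let whoever reviews safety say whether an event came from something the study did, and from what. This one asks only whether the event came from the biopsy. Four of the five listed sources of harm have no place in it, including the intervention under test (massage) and the disuse model (immobilization).

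Two consequences follow. Some expected, study-caused events cannot be coded properly at all. Others are measured against the biopsy because they happen to fall soon after it. Since the groups are biopsied on different days, relatedness ratings could then differ between groups for reasons unrelated to cause. This matters most for ordinary, expected events such as dizziness, chafing and soreness, where the rating is the main statement about cause. It also touches a study question: the Objectives section asks whether massage causes muscle damage, so a soreness rating that does not separate massage from biopsy is less useful.

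**Working it through.** The plan states no figure to reproduce. The check applies the four definitions to the protocol's own calendar.

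**Inputs**

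- Biopsies: days 2 and 9 in U-C, U-M and WB-M; day 9 only in WB-C (Study Design; Muscle Biopsies).
- Massage or sham: days 3, 5, 7 and 9 (Massage).
- Blood draws: days 2, 5, 7 and 9 (Heavy Water; Study Design, which gives the number as 3 to 4).
- Brace and crutches: day 2 to day 9, suspension groups only (Study Design).
- Heavy water: nine days, with the day-2 biopsy placed after the first two days of intake (Muscle Biopsies). Day 0 or day 1 is assumed for the first dose. Either precedes every biopsy, and days 2 to 8 are dosing days in both cases.

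**Events before a first biopsy.** Take dizziness after the first heavy-water dose and try each category.

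- Probable: no, it is not related to the biopsy.
- Possible: no, it does not follow a biopsy.
- Remote: no, it is not more than 7 days after a biopsy.
- Unrelated: no, a study procedure is not an extraneous cause.

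No category fits. The same reasoning covers any event in WB-C before day 9 that is caused by heavy water, a blood draw or the sham.

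**Events after a biopsy.** An event on day d meets the timing part of Possible for a biopsy on day b if 0 ≤ d − b ≤ 7, and on day b itself only if it arises after the biopsy. For b = 2 the window ends on day 2 + 7 = 9. For b = 9 it opens on day 9, so it includes nothing earlier. Counting scheduled days before day 9:

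| Procedure | Days before day 9 | In window: U-C, U-M, WB-M | In window: WB-C |
|---|---|---|---|
| First heavy-water dose | 0 or 1 (assumed) | none | none |
| Later heavy water | 2 to 8 | 7 of 7 | 0 of 7 |
| Blood draws | 2, 5, 7 | 3 of 3 | 0 of 3 |
| Massage or sham | 3, 5, 7 | 3 of 3 | 0 of 3 |
| Brace and crutches | 2 to 8 | 7 of 7 (U-C and U-M) | not applicable |

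Day 9 is also inside the day-2 window (9 − 2 = 7). Once the day-9 biopsy is done, all four groups are in a window, so the divergence runs from the day-2 biopsy to the day-9 biopsy.

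**Same event, two groups.** A bruise at the blood-draw site on day 5 is 5 − 2 = 3 days after a biopsy in WB-M and meets the Possible window. In WB-C it precedes the only biopsy by 9 − 5 = 4 days and does not. Cause and day are identical; only the biopsy schedule differs.

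**Do symptoms settle it?** Not reliably. Pain, bleeding and infection are listed for both biopsy and blood draws, and soreness for biopsy, blood draws, massage and brace. The brace is on the left leg, so soreness of the non-immobilized leg means the right leg, which is the leg biopsied on day 2.

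**The case against.** The strongest reply is that little depends on this scale. Adverse events are monitored in real time whatever their cause. Serious events go to the IRB and the clinical research center within 24 hours verbally and 48 hours in writing; unanticipated events reach the IRB within 48 hours. Annual reports are not limited to biopsy events, and the monitoring board reviews adverse events, reports every six months and can audit. Intensity is graded separately, and the SAP has no adverse event outcome. All of this stands and confines the fault to causality coding.

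Second, Possible expressly allows for other factors, so it is a weak statement about the biopsy rather than a false one. That also stands, but the category does not record which factor, and it is unavailable before a biopsy.

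Third, Remote could be stretched to pre-biopsy events by ignoring its 7-day parenthesis. A harm of the study's own tracer would then carry a label meaning unlikely to be related, which is no better.

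Fourth, the biopsy focus has a reason: the protocol says the monitoring board is in place because of the biopsies. That explains the wording but does not supply the missing categories.

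A reader might go further and infer that the scale systematically misattributes harms and hides them from the monitoring board and IRB. The documents do not support this. No reporting duty turns on the rating, and for pre-biopsy events the defect is a gap in coverage, not a wrong attribution. Rating a post-biopsy event Possible points toward a study procedure rather than away from one. Nor is it right that every event from day 2 to day 9 falls in the window: WB-C is excluded, as are events before the biopsy on day 2.

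**Conclusion.** The concern holds, limited to causality coding. Followed as written, the scale gives no fitting category to a study-caused event before a first biopsy, and it treats every event after the day-2 biopsy through day 9 in U-C, U-M and WB-M as meeting the timing test for Possible, without naming the procedure responsible. Before day 9, all three massage or sham days and all three blood-draw days are in the window in WB-M (on day 2, after the biopsy), and none are in WB-C. This is more than missing detail, because a stated rule gives group-dependent ratings for the same event.

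The conclusion describes what the rule yields, not an observed error. The continuation review mentions one previously unreported adverse event in 12 months but gives neither its nature nor its rating, and the adverse event form and monitoring reports were not provided. It assumes that no other attribution scale is in use, that the 7-day window is counted in calendar days, and that the first heavy-water dose is on day 0 or day 1. No efficacy result is affected.

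**What to change.** - Reword Probable, Possible, Remote and Unrelated to refer to any study procedure: heavy water, blood draw, immobilization and crutches, massage or sham, and biopsy.
- Record for each event the procedure to which it is attributed, with timing counted from that procedure.
- Apply the scale identically in all four groups, including before any biopsy.
- Check the events already recorded against the revised scale and re-rate those whose rating changes.

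The cost is a small protocol amendment, possibly one added field on the adverse event form (which may already have it), and a check of recorded events, whose total number is not given. The demographic table in the continuation review adds to 1 + 3 + 5 + 38 + 2 = 49 enrolled, so the check covers a modest number of participants. No study procedure or schedule changes.
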